7. TRAINING PLAN

7.1. Training Plan for Research Device/Product

Study Staff will be trained on the use of device system, its components, and Sponsor-provided accessories such as the Sponsor-provided patient monitoring equipment. The Sponsor will provide initial instructions for use of the device and swaddles and, as necessary, subsequent training on any changes to the device, including any necessary storage and handling requirements, preparation for use, any pre-scan checks of safety and performance and any precautions to be taken after use, (e.g. disposal).

No training will be conducted on human subjects.

7.1.1. MR Procedure Documents

The PI is responsible for ensuring that all MR scan operators that will be operating the research device will be made aware of and, if necessary, provided training on scanning procedures at the beginning of the study and after any new version of the *MR Procedure Document* is released by the Sponsor to the investigational site

7.1.2. Configuration Changes

The PI is responsible for ensuring that all MR scan operators that will be operating the research device will be made aware of and, if necessary, provided training on device configuration changes released by the Sponsor to the investigational site.

7.2. Training Plan for Protocol

Study staff will be trained on the Study protocol and Study procedures, including completion of Informed Consent Forms (ICFs), Case Report Forms (CRFs), *MR Procedure Documents*, and other study documentation.

Training will also be provided to ensure appropriate storage and handling of images and data. All study staff will be required to be trained on Good Clinical Practice (GCP) guidelines per ISO 14155:2011.

A record of all formal training attendance and date conducted will be stored in the Site Regulatory Binder and provided to the Sponsor for inclusion in the Sponsor's Clinical History File (CHF).

8. DATA ANALYSIS AND STATISTICS

8.1. Statistical Analysis Methods

8.1.1. Sample Size Determination

Based on the literature, studies including low birth weight neonates commonly assume a 20% dropout rate²⁸ Compared to gold standard, approximately 82% of images attained from neonates/infants with MRI are diagnostically useful (evaluable) in part due to subject movement during scanning²⁹ The enrolment quota calls for 30 (Phase 1) and 5 (Phase 2) evaluable image sets. More than one image set may be collected from a single subject; however, this case is exceptional and may not be common.

This study requires a population N such as that:

$$0.82N - (0.82 \times N)(0.2) = (30 \text{ phase 1} + 5 \text{ phase 2})$$

To satisfy this requirement, a minimum population size $N=53$ is required. This is approximated upwards to $N=60$ to account for unforeseen contributions to dropout or evaluable image rates in sensitive neonate and infant populations. It is prospectively expected that Phase 1 of this study may be ended early if required data for engineering purposes is collected before the maximum number of subjects enrolled; it is also prospectively expected that Phase 2 of this study may be ended early if required data for regulatory submission is collected before the maximum number of subjects are enrolled in this Phase. Any determination to end the study before the expected number of subjects has been enrolled will be provided by the Sponsor, in writing, to the investigational site.

8.1.2. Statistical Analysis Methods

As necessary to support regulatory submission, continuous variables will be summarized with standard descriptive statistics including counts, means, standard deviations, medians, and minimum, maximum. Categorical variables will be summarized with frequencies and percentages.

8.1.3. Other Analysis Methods

Images and associated data being collected in this study are intended for use on a per-subject basis for engineering purposes.

Upon completion of this study, the Sponsor's authorized research and engineering program may utilize data collected in this study in full or in part for authorized engineering purposes.

The principal investigator (PI) at each site may be asked to provide electronically tabulated data summaries for subject demographics and other descriptive data summarizing study results. PI-prepared data tabulations will not be controlled or verified by the Sponsor. These results are collected for learning purposes only, and any PI-provided data tabulations will be summarized in the final study report for reference only. Any direct or derived results from PI-prepared data tabulations will not be used by the Sponsor for regulatory submissions.

8.2. Interim Analysis

There are no interim cohort-based statistical analyses for this study. At the Sponsor's discretion and per local EC/IRB requirements, the status of enrolment and other subject data may be summarized at any time determined by the Sponsor during this study.

8.3. Handling of Missing Data

The Sponsor may descriptively summarize the primary performance and safety endpoints from Phase 1 and Phase 2 of this study, including the descriptive statistical summary of patients that exhibit a body temperature rise of more than 0.5°C from acclimated pre-scanning baseline body temperature (resulting in an Expression Monitor alarm during scanning). If the Sponsor observed that the dataset for any subject is incomplete, additional clarification from the investigator may be requested. The Sponsor may additionally request copies of any clinical imaging datasets (including MRI scan datasets and other clinically indicated imaging examinations) that are conducted as follow-up to unexpected findings observed in this study.

8.4. Pass/Fail Criteria of the Study

The study will be considered successful if sufficient evidence is collected to inform the performance and safety of the 3.0T Neonatal MRI investigational device in a representative population of neonates and/or infants, in accordance with Annex X of the European Medical Device Regulation.

9. OTHER INTERIM ACTIVITIES (QUALITATIVE INTERIM SUMMARIES)

9.1. Phase 1 Qualitative Investigator Summary

For Phase 1 of this study, the PI is responsible for preparing qualitative Interim Summaries based on meetings between the Sponsor and investigator, as described in Section 9.1. Phase 1 Qualitative Investigator Summary (Phase 1 only).

These documents, along with images and data collected to date, will provide a basis for the Sponsor's determination of *MR Procedure Document*.

9.2. Phase 1 and Phase 2 End-of-Phase Interim Reports

A total of two End-of-Phase Interim Reports will be prepared by the PI at the end of enrolment for Phase 1 and at the end of enrolment for Phase 2. The PI will descriptively summarize the subject population and imaging results collected to date. This may include data tabulations, at the discretion of the PI. The Phase 1 End-of-Phase Interim Report may be considered by the Sponsor in decision-making activities required for Phase 2, and may be summarized in the Sponsor's final clinical study report. PI-prepared data tabulations will not be controlled or verified by the Sponsor. These results are collected for learning purposes only, and any PI-provided data tabulations will be summarized in the final study report for reference only. Any direct or derived results from PI-prepared data tabulations will not be used by the Sponsor for regulatory submissions.

10. DEVIATIONS

10.1. Management of Protocol Deviations

All human MR scanning with the investigational device used in this study must be conducted under a current *MR Procedure Document* version. If any clinical scan procedure is conducted that is not compliant with the current *MR Procedure Document* version it will be considered a deviation and should be reported according to the following guidelines

Deviations to the protocol may occur when necessary to protect the life or physical well-being of a subject

Except in an emergency, prior approval by the Sponsor is required for changes in or planned deviations from this protocol

If these changes affect the scientific soundness or the safety and welfare of the subject, prior EC/IRB approval is also required

Planned Protocol Deviation documentation must be filed in the Site Study Regulatory Binder

There are two types of unplanned protocol deviations, critical deviations and non-critical deviations

All deviations must be documented and reported, the criticality of the deviation will determine the reporting path

Critical Deviations:

Deviations that significantly affect the safety, efficacy, integrity or conduct of the study

These deviations must be reported to the Sponsor no later than 5 working days from awareness of occurrence and reported to the EC/IRB per the deviation reporting policy.

If an Investigator uses a device without obtaining informed consent, the Investigator shall consider this a critical deviation and report the event to the Sponsor and the EC/IRB within 5 working days of the occurrence.

Non-Critical Deviations:

Protocol deviations that DO NOT significantly affect the safety, efficacy, integrity or conduct of the trial.

These deviations must be documented on the Case Report Form Protocol Deviation page and will be reviewed by the study monitor.

11. COMPLAINT HANDLING AND ADVERSE EVENT REPORTING

11.1. Foreseeable Adverse Events and Device Effects

MRI is generally considered safe for adults and babies because it does not involve exposure to ionizing radiation, such as x-rays. MRI of 4T or less is considered non-significant risk for infants and neonates, and population-specific risks are well described.^{26,30,31,32,33,34,35} The known risks typically associated with 3T MRI scans in this study are listed below and have been mitigated by the Sponsor to levels that are as low as reasonably practicable (ALARP), to levels equivalent or less than MRI using commercially released scanners:

Movement of Metal Objects Magnetic fields in MRI can cause internal or external ferrous metal (e.g. implants, umbilical cord clamps, oxygen tanks, infant security bands, scissors, paperclips, and pens) small enough to be innocuous to adults to move or become projectile, leading to minor injuries like cuts/bruises and, in rare cases, serious injury or death.

Thermal Effects Body temperature can change due to environmental cooling and/or MRI radiofrequency (RF) warming. Typical specific absorption rates (SAR) during study MRI scanning are not expected to cause injury. In rare cases, serious burns can occur that are typically related to metallic object presence or improper patient positioning.

Semi-permanent Cable/Device Removal Chest leads and other semi-permanent attached cables/devices can warm and electronics can function abnormally, potentially causing discomfort, injury, interruption of care, and, in rare cases, serious destabilization. Devices not known to be safe in the MRI environment may be removed or replaced when doing so does not detrimentally impact normal medical care, otherwise the subject will be withdrawn.

Peripheral Nerve Stimulation Transient skin sensations ('tingling') or peripheral nerve stimulation (PNS) is related to dB/dt and gradient rise time, and is expected to be rare in neonates and infants due to small skin surface area and conservative device thresholds. Subjecting infants to sudden, rapidly changing gradient magnetic fields during imaging can, induce circulating currents in conductive tissues of the body that typically are not painful and resolves spontaneously, though, in theory, discomfort or pain from PNS in infants is possible.²⁶

Acoustic Noise High noise levels in the scan room and in the bore of the scanner during MRI scanning may cause discomfort but are not normally hazardous with proper hearing protection. Spontaneously resolving hearing loss or tinnitus typically related to improper hearing protection can, in rare cases, become chronic or severe. Hearing protection

(combination of earplugs or ear plugs combined with earmuffs to achieve noise reduction of ≥ 22 dB is mandatory during MRI in this study)

Adverse Effects due to Delay of care Though discontinuation of study procedures for urgent medical care is not anticipated, unexpected urgent care may be delayed due to removal from the MRI of other study devices. The expected delay is only a few minutes, but there is a risk that any amount of delay could detrimentally impact urgent medical care.

In addition, there are possible but not anticipated risks that have been identified for the Neonatal MRI device during development. These risks have been identified and mitigated to levels ALARP by the Sponsor and are described as follows:

Airflow Interruption: In rare cases, blockage of the bore of the investigational 3.0T Neonatal MRI device, particularly at the head end of the scanner, can cause interruption of normal airflow in the bore of the scanner. Through proper measurement of the subject, combined with visual inspection of the bore of the scanner once the subject is placed in the scanner, the scan operator will ensure that no blockage of the bore of the MR scanner exists.

Swaddlerisk: Compression by the swaddle can cause discomfort and, in rare cases, serious injury usually due to study procedures not being followed.

Fall: During transport or scanning, infants and neonates may be at increased risk of fall from the height of the MRI table or transport devices, typically due to improper use. The risk of fall is not expected to be greater than in routine transport and the height of all device components complies with regulatory requirements.

Like routine MRI scanning of <4.0T MRI procedures conducted with the 3.0T Neonatal MRI investigational device rarely cause harm when performed as directed by trained staff using appropriate procedures as described in this protocol device documentation and in Sponsor provided training. The risks of AEs and SAEs have been mitigated by the Sponsor to levels ALARP. If the Sponsor learns any new information that would increase the risk to subjects in this study, the PI will be notified in writing.

11.2. Adverse Event Definitions

Adverse Event (AE) as defined by EN ISO 14155-2011: any untoward medical occurrence, unintended disease or injury, or untoward clinical signs (including abnormal laboratory findings) in subjects, users or other persons, whether or not related to the investigational medical device.

Serious Adverse Event (SAE) as defined by EN ISO 14155 – 2011: an adverse event that

- (a) led to death;
- (b) led to a serious deterioration in the health of the subject, that either resulted in:
 - (1) a life-threatening illness or injury, or
 - (2) a permanent impairment of a body structure or a body function, or
 - (3) in-patient or prolonged hospitalization, or
 - (4) medical or surgical intervention to prevent life-threatening illness or injury or permanent impairment to body structure or a body function;

(c) led to fetal distress, fetal death or a congenital abnormality or birth defect.

Anticipated: Any adverse event and/or reaction, the specificity or severity of which is consistent with the EC/IRB approved informed consent, protocol, investigator brochure, or product labelling.

Unanticipated adverse Device effect: Any serious adverse effect on health or safety or any life-threatening problem or death caused by, or associated with, a device, if that effect, problem, or death was not previously identified in nature, severity, or degree of incidence in the investigational plan or application (including a supplementary plan or application), or any other unanticipated serious problem associated with a device that relates to the rights, safety, or welfare of subjects.

11.3. Management of Adverse Event Reporting

Any adverse events will be recorded in the subjects study record and the Adverse Event Case Report Form. The following information should be obtained:

- Description of Event
- Date of onset and resolution
- Intensity (mild, moderate, severe)
 - **Mild:** Symptom(s) barely noticeable to the subject or does not make the subject uncomfortable. The AE does not influence performance or functioning. Prescription drugs are not ordinarily needed for relief of symptom(s).
 - **Moderate:** Symptom(s) of a sufficient severity to make the subject uncomfortable. Performance of daily activities is influenced. Treatment of symptom(s) may be needed.
 - **Severe** Symptom(s) of a sufficient severity to cause the subject severe discomfort. Treatment for symptom(s) may be given.
- Serious (yes/no)
- Relationship to device (unrelated, possibly related, probably related)
 - **Unrelated:** The adverse event is reasonably expected to be related to (or caused by) a concurrent illness, effect of another device/drug or other cause, and is unlikely related to the investigational product
 - **Possibly related:** The adverse event is reasonably expected to be related to the investigational product, and an alternative aetiology is equally or less likely compared to the potential relationship to investigational product
 - **Probably related:** There is a strong relationship to investigational product, or recurs on re-challenge, and another aetiology is unlikely, or there is no other reasonable medical explanation for the event.
- Treatment given and/or action taken (procedure stopped, withdrawn from study, no action)
- Anticipated (yes/no)

Adverse events that occur during a subject's active enrolment (as described in Section 6.3.1. - Pre-MR Scanning Activities: Duration of Active Enrolment) will be reported to the local EC/IRB per their policy and, if applicable, to regulatory agencies. Medical events that occur outside of

the active study during observational data collection, such as during standard of care follow-up conducted for any unexpected findings, will not be considered study adverse events.

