1.4. Device Risk Analysis

1.4.1. Risks

The 3.0T Neonatal MRI investigational device is intended for use in neonates and infants, and its components and accessories used in this study are based on similar commercial systems labelled for use in patients aged greater than 2 years of age and manufactured by the Sponsor, and these devices have undergone non-clinical qualification and risk assessments conducted by the Sponsor. Participating in this study involves some risks that are unique to the design of the scanner and population (neonates and infants), as described [Section 11.1 Foreseeable Adverse Events](#). This section lists possible foreseeable adverse events and device effects, but actual occurrences of these risks are uncommon and are not anticipated to occur frequently, if at all, in this study. While serious adverse events can occur in MRI exams in rare cases, typically with adverse events occurring as a result of failure to correctly follow routine site MR safety procedures for scanning, no serious adverse events are anticipated in this study.

Subjects participating in research MRI scanning in this study are not expected to be at increased discomfort or risk beyond that posed by other standard of care MRI devices. The investigational single-use disposable swaddle is a medical device that is expected to have risk comparable or less than routine MR padding, blanketing, and/or other transportation devices. During the study, the subject will be transported and cables or other devices may be disconnected or connected, which could cause discomfort or interruption of care. The investigator is responsible for ensuring minimal disruption of normal care during the study.

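### The adverse-event causality scale in section 11.3 leaves a gap between its levels and offers no way to attribute harm to study procedures

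*Combined protocol and SAP*

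**What the plan says.** Section 11.3 lists what is recorded for each adverse event. The only causality item is "Relationship to device (unrelated, possibly related, probably related". Each level is worded against the investigational product, a term that sections 11.2 and 11.3 do not define.

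- *Probably related*: a strong relationship, with any other cause unlikely.
- *Possibly related*: the condition set is "The adverse event is reasonably expected to be related to the investigational product, and an alternative aetiology is equally or less likely compared" with the device explanation.
- *Unrelated*: the event is attributed to "a concurrent illness, effect of another device/drug or other cause, and is unlikely related to the investigational product".

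Elsewhere the protocol foresees harm from taking part that need not come from the scanner itself. Section 1.4.1 warns that "the subject will be transported and cables or other devices may be disconnected or connected, which could cause discomfort or interruption of care". Section 2.3 accepts the ordinary risks of moving a baby away from its usual care area. Section 11.1, under cable and device removal, describes effects "potentially causing discomfort, injury, interruption of care, and, in rare cases, serious destabilization", and under delay of care it says that "there is a risk that any amount of delay could detrimentally impact urgent medical care".

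Section 3.4.1 bases the primary safety endpoint on rates of adverse events. Section 11.2 counts an adverse event regardless of device relatedness.

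**The concern.** A causality scale should give every event exactly one level, and its axes should cover the sources of harm that the protocol itself names. This one appears to fail on both counts.

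It matters because the study has a single arm and no comparator (4.1.1), and all subjects are inpatients (5.4, 6.5). A raw adverse-event rate in that population says little about the device without a judgement of cause, and this field is the main place where the judgement is recorded. The same judgement bears on unanticipated adverse device effects, which 11.2 defines as events caused by or associated with a device. The scanner and the swaddle are also separately classified devices (2.4), and 11.1 lists a separate compression risk for the swaddle, yet they share one rating.

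**Working it through.** No arithmetic applies and the plan states no figure to reproduce. The check is whether the three definitions cover all cases.

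**Step 1: coverage of the scale.** Cross the likelihood of a device role with the relative likelihood of another cause.

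| Case | Device role | Other cause | Level that fits |
|---|---|---|---|
| 1 | Unlikely | Present | *Unrelated* |
| 2 | Reasonably expected | Equally or less likely | *Possibly related* |
| 3 | Strong | Unlikely | *Probably related* |
| 4 | Plausible, not unlikely | More likely | None |

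Case 4 fails *Possibly related* because that level requires that "an alternative aetiology is equally or less likely compared to the potential relationship to investigational product". It fails *Unrelated* because the device role is not unlikely. It fails *Probably related* because another cause is likely. Two raters could code such an event differently without either having a definition to follow. A rater could close the gap by reading unlikely as merely less likely than the alternative, but that would move plausible device contributions into *Unrelated*.

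**Step 2: procedural harm.**

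- *No likely device part.* Section 6.3.1 allows transport to the MR suite in the incubator or crib, and leads may be disconnected for the scan. Harm arising only from these steps meets the *Unrelated* definition, through the reference to another device or other cause. No other level fits.
- *A study component is involved.* The transport cart is described among the device components (2.1.2), and the swaddle is an investigational device designed for transfer (2.1.3). Section 11.1 links delay of urgent care to removal from the MRI or study devices. Such events could be rated possibly or probably related, depending on how the rater reads the undefined product.

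**Step 3: is the gap filled elsewhere?** Adverse events are collected from first use of the sizing tool until return to the care environment with all study devices removed (6.3.1), so transport and cable events fall inside the window. I found no item on relationship to study procedures. Section 11.5 (device complaints) and the AE CRF were not in the text available to me, and nothing here relies on them.

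**The case against.** The strongest reply is that this is a data-capture detail in a descriptive study with no hypothesis (3.1), and that it does not reach the endpoint. Much of that stands, and several stronger readings should be set aside.

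- **That the safety summary for CE mark will understate harm.** A reader might infer this, but the documents do not support it. The primary endpoint counts all adverse events (3.4.1, 11.2), an event rated *Unrelated* still counts, and sections 8.1.2 and 8.3 plan no rate of related events. Reporting of SAEs to the sponsor (11.4) is not limited to related events either.
- **That transport, cable-removal and delayed-care harms are all coded *Unrelated*.** There is no such rule. *Unrelated* also requires a device role to be unlikely. The cart and swaddle are study devices, the cable hazard includes warming and abnormal function during MRI, and delay is tied to removal from the MRI or study devices. Only harm with no likely device part is forced into that level.
- **That *Possibly related* is a more-likely-than-not test.** It accepts an equally likely alternative. With several candidate causes, none likelier than the device, an event can qualify with the device below an even chance.
- **That most events will fall in the gap.** Nothing shows this. The collection window is short, scanning is capped at 60 minutes, subjects may be admitted only for observation, and hazards such as swaddle compression, a fall or noise would often have no competing illness.
- **That scanner, swaddle and procedure effects cannot be separated at all.** The event description, swaddle use and timing, transport mode (6.3.1) and component issues (Table 3) allow some reconstruction. SAEs also use a separate sponsor form whose content is not given.

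What this leaves untouched is the wording. Case 4 has no level, and purely procedural harm has no route to a related rating. Reconstruction after the event is a weaker substitute for a clinician's recorded judgement.

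**Conclusion.** The point holds as a defect in how cause is recorded. The scale is not exhaustive, the product it refers to is undefined, and harm from study procedures without a likely device role can only be called *Unrelated*, even though sections 1.4.1, 2.3 and 11.1 foresee such harm. The overall adverse-event rate is unaffected. What is affected is any attribution of harm to the scanner, the swaddle or study participation, and potentially the identification of device effects under 11.2.

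I put no percentage on this, because the documents give neither an expected number of events nor a planned related-event rate. The conclusion rests on reading the 11.3 definitions literally and on the AE CRF carrying no causality items beyond those listed there. The change is worth making because attribution is the main way to interpret adverse events without a comparator.

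**What to change.** In section 11.3 and on the AE CRF:

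1. Record relationship separately to (i) the MRI system, stating that the cart, padding and accessories are included, (ii) the swaddle, and (iii) study procedures, meaning transport, lead and cable handling, and interruption of care.
2. Redefine *Possibly related* as a causal contribution that cannot be ruled out, even if another cause is as likely or more likely, and *Unrelated* as a contribution that can reasonably be excluded. Keep *Probably related* as it is. Every event then has a level on each axis.
3. Alongside the all-event rate, tabulate events rated possibly or probably related to a device or to a procedure.

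The cost is a rewording of 11.3, a few extra CRF items per event and one more descriptive table. The number of events rated related may rise, and the report should say that the definition is deliberately inclusive. No clinical procedure changes.
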